flyers may also be posted generally in areas where potential participants may see the information (i.e. local chapters of Veterans Organizations, SCI sporting events) and included in newsletters or journals with a focus on the SCI population. Each site is expected to prescreen at least 100 potential participants. Pre-screened eligible and interested potential participants will be referred by the Site ReWalk Trainers and/or Site Coordinators for initiation of the consenting process and scheduling of the screening evaluations. The *screening evaluations* will be performed only in consented participants by the Site Investigator, other Site Physician(s) and/or the site study team. These screening evaluations are for the inclusion/exclusion criteria for medical, physical and health-related eligibility. The screening evaluations include a history and physical examination (H&PE), a specific history of fragility fractures, unhealed traumatic fractures, swelling, bruising, redness, or other abnormalities of the lower extremities, International Standards for Neurological Classification of SCI (ISNCSCI) examination for neurological level and function [formerly called American Spinal Injury Association (ASIA) or American Spinal Injury International Standards Scale (AIS) examination], a BMD scan and a lateral foot x-ray of each calcaneus with potential for a clinical referral for a CT scan for further evaluation, if recommended. Participants who pass the inclusion/exclusion criteria will then undergo a home evaluation and companion identification for continued eligibility. The potential participant may have up to three companions who share in the EAW training with the participant. All companions will be provided a separate consenting process and will either sign an informed consent form or assent over the phone to be enrolled. Baseline evaluations will be performed only in those participants who have passed all screening criteria to this point. Once the baseline evaluations are completed, all participants will be fitted for the ReWalk and begin a five-session basic EAW training course. In order to avoid a biased group selection, all participants will be trained for five sessions of EAW basic skills. The EAW basic skills training will be conducted at the VA hospitals at fifteen sites, in the Community Based Outpatient Centers (CBOCs) under the same Federal Wide Assurance (FWA) as the sites, or in the participant's home/community. Only those who pass the EAW basic skills test (and all other screening criteria) will be eligible to be randomized to either the Intervention or Control group. Each site is expected to consent and screen at least 60 potential participants and randomize 4-24 participants for an overall 160 randomized across 15 sites.

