
B. Randomization System

An Interactive Touch Tone Randomization System (ITTRS) will be used for randomization within

each site. This system will be accessed through the Cooperative Studies Program Coordinating Center at the Perry Point VA Medical Center, [name].

C. Population to be Studied

One hundred-sixty male or female Veteran or active duty military personnel with chronic SCI, of \geq six months duration, who are \geq 18 years of age, and who are medically stable and wheelchair users for indoor and outdoor mobility, will be eligible for screening to be enrolled in the study. All potential participants will be Veterans or active duty military personnel with SCI who are affiliated with or transferred to one of the fifteen VA SCI Services that will be participating in this study. Study participants will generally be outpatients with the exception of those inpatients who meet the eligibility criteria and are approved by the Site Investigator (e.g., some inpatients may have been admitted for a wheelchair fitting or another non-medical reason). Non-veterans, other than active duty military personnel getting treatment at the VA, will not be eligible to participate. Eighty participants will receive SOC plus EAW (Intervention group) and 80 will receive SOC (Control group). It is expected that no more than 15% of the participants will withdraw early (dropout rate) and this attrition rate is expected to be evenly distributed between the two groups (12 withdrawals/group). One hundred-thirty-six participants are expected to complete the study (68/group).

V. INTERVENTION AND METHODS OF TREATMENT

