Intervention Group: Training for the Intervention group will consist of 25±5 sessions of EAW training followed by an EAW Advanced Skills Test that will determine the eligibility of the participant to take the device home. Training will take place at the VA hospitals, in the CBOCs under the same FWA as the sites, or in the participant's home/community. Participants in the Intervention arm will take the device home to use. During the training and home/community use components of the study, the built-in step counter on the device will record the weekly total number of steps taken. The EAW Activity Log will be completed by each participant on a weekly basis to record the location, duration and frequency of device use. The Trainers will follow up weekly with the participants for completion of this task.

Control Group: In order to provide a similar level of attention to the Control group during the Orientation/Training phase, the Control group will receive interviews to identify types of physical activities in which they usually participate. Control participants will be instructed to complete the Usual Activity Log on a weekly basis during the Orientation/Training course and during the four-month Intervention phase. Weekly contact by the study team will be provided to the Control group during the Orientation and Intervention phases, in person, over the phone, or through secure messaging using My HealtheVet.

IX. OUTCOME MEASUREMENTS

The frequency and specific time points of each of the outcome measurements can be found in the "Training and Testing Schedules" (Table 6).

The two primary, major secondary and secondary outcomes are measured at baseline, post Orientation/Training phase, post 2-month Intervention phase, and post 4-month Intervention phase. The main comparison for the two primary and major secondary outcomes is the change in

the outcome measures from baseline to post 4-month Intervention phase.

A. Primary Outcomes

1. Mental Health Component Summary (MCS) of the Veterans Rand-36 (VR-36) for Vitality, Social Functioning, Role-Emotional, and Mental Health.
2. The sum T-score for the SCI-QOL Physical Medical Health domain (three item banks of Bladder Management Difficulties, Bowel Management Difficulties, and Pain Interference).

B. Major Secondary Outcome

1. Total body fat mass (by DXA scan) (results will be blinded)

C. Secondary Outcomes

1. Global Impression of Change Scale (Participant- and Companion-rated);

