 - c. Walk tests and mobility assessments are recorded during each session once the participant is able to perform them and for the duration of the Training phase for the:
 - i. 10 meter walk test for time (10mWT),
 - ii. 6 minute walk test for distance (6minWT), and
 - iii. Timed-up-and go (TUG).
 - d. Walk tests and mobility assessments are recorded at months 2 and 4 during the Intervention phase as an outpatient visit.
3. Exit survey: participants and companions will be asked questions about their satisfaction with the study overall, and specifically about the device and training.
 - a. Previously randomized participants and their companions will be called to complete the "Exit Survey".

F. Methods for Obtaining Outcome Measures Data

The Site ReWalk Trainers and Assistant ReWalk Trainers will perform the mobility skills and walking tests and be responsible for recording the EAW data. Exoskeletal-assisted mobility walking test assessments are measured in distance and/or time. Other mobility skills such as arresting gait on command, maneuvering to a wall rest, navigating doors, etc., will be scored one session per week as “able” or “unable” to perform the task; in addition, the level of assistance needed to complete the task will be recorded with each assessment.

The Site Coordinator will be responsible for administering the QOL outcome assessments (VR-36, SCI-QOL, Global Impression of Change Scale (Participant- and Companion-rated), PROMIS Sleep Disturbance, SCI-FI, and bowel function surveys) through in-person or phone interviews. The Site Coordinators will record all answers on the fixed forms. The site Trainers may assist as back-up QOL assessors only if necessary. In order to have continuity of assessment, the Site Coordinators will administer the surveys at all of the time points. Each SCI-QOL, PROMIS Sleep Disturbance and SCI-FI survey is reported as a T-score (mean=50, SD=10). The VR-36 is in a fixed form and administered sequentially.

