1 or 2 sided test?	2	2	2
Control proportion, π_1	0.100	0.100	0.100
Intervention proportion, π_2	0.333	0.420	0.350
Odds ratio, $\psi = \pi_2(1 - \pi_1) / [\pi_1(1 - \pi_2)]$	4.493	6.517	4.846
Power (%)	80	95	85
n per group	67	60	66
n per group with 15% attrition	79	71	78

C. Feasibility Phase

In order to confirm the hypothesized control proportion for the two primary and major secondary outcomes, to determine the feasibility of recruiting participants at each site, and to assess other operational aspects of the study, a feasibility phase has been built into this study. The planned duration of the feasibility phase of the study is one year. Six out of fifteen planned sites (including three sites that are designated CSP NODES) will be brought up in the first year.

During the feasibility phase, several site start-up activities and operational aspects of the study will be examined. These activities will include the hiring of site personnel (including classification of position descriptions, position announcements and recruitment), the processes for procuring and distributing the ReWalk and iDXA devices to the sites, the methods by which site staff are trained on the use of the devices and on data collection and management activities, the number of sessions needed for participants in the intervention group to pass the Advanced Skills Test, the practicality of Veterans or members of the military with SCI to find motivated and eligible walking companions, and attrition (drop-out) rates. The lessons learned during this phase will be implemented during activation of the remaining participating sites.

Recruitment rates at the six active sites will be closely monitored during this phase. The initial six sites are expected to enroll a total of 48 participants by the end of the first year. The actual recruitment experience of the six sites in the first year will be used to revise the projected recruitment rate for the remainder of the study and may lead to a lengthening or shortening of the total recruitment period, as appropriate.

Besides the verification of the assumed recruitment rate and other site start-up activities, the feasibility phase also provides an opportunity to assess the assumed success rates in the control (SOC) group. As stated above in section II, we have hypothesized that 10% (0.100) of the control

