group will have a clinically meaningful change in the outcome measures for sample size/power calculations. Ten percent is thought to be a conservative estimate as there is no reason to expect the control group to have clinically meaningful changes in quality of life measures or in total body fat mass while continuing to receive SOC for their spinal cord injury. However, as a means of verifying the control proportion of 10% (or 0.100), the proportion of participants considered successful in the control group for all three outcomes and 95% confidence intervals for the proportions will be reviewed upon the completion of the feasibility phase. Based on the extensive experience with this population it is highly unlikely that the assumed success rates in the control group (SOC) will be any higher than the assumed 10%.

At the completion of the feasibility phase, the study will be moved to a continuation phase where the remaining sites (9 remaining sites) will be activated and the remaining participants will be recruited.

D. Baseline Comparability

Baseline comparability between the treatment groups will be evaluated with respect to such variables as demographics (e.g., age, gender, and race) and baseline values of outcome measures (MCS/VR-36, SCI-QOL, total body fat mass, etc.). Chi-square and analysis of variance techniques, as appropriate, will be used to determine any differences in distribution of the variables across the treatment groups. Any variable that appears to be different between the groups ($p < 0.10$) will be considered as a potential covariate in statistical analyses.

E. General Outcome Analysis Guidelines

All statistical tests will be 2-sided. The two primary and major secondary outcome measures will be tested at a 0.025 level of significance. Because of the large number of secondary outcomes to be analyzed, all other secondary outcomes will be tested at a significance level of 0.01 to maintain control over Type I error. SAS 9.4 will be used to conduct all the statistical analyses. A variety of analytic methods will be used for the primary endpoints, secondary endpoints and other analyses.

F. Analysis of Primary and Major Secondary Outcome Measures

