The primary analysis will be based on an intent-to-treat (ITT) model. All participants who are randomized will be included for both groups, whether they are study completers (participants who complete the study through the four-month intervention phase) or early terminators (drop-outs). In order to test the hypotheses for the primary and major secondary outcome measures, each randomized participant will be deemed a success or failure at attaining: 1) ≥ 4.0 point improvement in the MCS of the VR-36, 2) $\geq 10\%$ improvement in the SCI-QOL bladder management difficulties, bowel management difficulties and pain interference sum T score, and

3) ≥ 1 kg. total body fat mass loss. For each of the outcomes, the proportion of participants successful at achieving a clinically significant improvement will be compared between the two groups (Intervention vs. Control) using a chi-square analysis. These will constitute the primary and major secondary efficacy analyses. Participants who drop out will be treated as failures. As such, by design, there will be no missing data: participants either meet the outcome criteria (successes), do not meet these criteria (failures) or they drop out (also failures).

G. Secondary Analyses

In addition to the primary analysis, several secondary analyses will be performed and are described below.

1. Analyses will be performed that include only those participants who complete the study (excluding drop-outs):
 - a) Chi-square analyses of the primary and major secondary outcome measures (proportion of successes) will be repeated for only those participants who complete the 4-month intervention phase.
 - b) Analyses of the MCS/VR-36, SCI-QOL, total body fat mass loss, Global Impression of Change and other secondary outcome measures will include comparisons of the mean difference scores (change from baseline to the end of the intervention phase) of these outcome variables using t-tests.

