2. Interim time points of data collection for all outcome variables have been incorporated into the study design. These time points are: baseline, after training/orientation phase, two months into the intervention phase, and then again after four months of the intervention phase (primary and major secondary outcomes main time point). Secondary analyses of the MCS/VR-36, SCI-QOL, total body fat mass loss, Global Impression of Change and other secondary outcome measures will include comparisons of the mean difference scores (change from baseline to the end of each time point) of these outcome variables using t-tests. Other secondary analyses of outcome measures will be performed that use the all data available. For these continuous variables, repeated measures analysis of covariance will be used to analyze them, with baseline scores, plus any variables determined from the baseline comparisons, being used as covariates in the analyses. SAS MIXED and GENMOD procedures, which allow for the use of incomplete data sets, will be used if it can be safely assumed that missing data are missing at random. If this assumption is not valid, a multiple imputation strategy of the missing responses will be implemented which does not rely on the assumption that missing data occur at random. This will allow an intent-to-treat approach for the statistical analyses, where complete cases are not required.

3. An analysis to determine the characterization of the drop-outs will be performed by using descriptive and correlation statistics. The reasons for drop-out and the number of sessions/time points completed will be described. A correlation analysis will be performed with the reasons for drop-out and the demographic variables and other potential variables to identify characteristics of persons who drop out of the study.

H. Monitoring of Study by Study Group and Executive Committee

The Study Group (all of the Site Investigators) and Executive Committee will meet 6 to 9 months after patient recruitment begins and at annual intervals thereafter until the end of the study. Three weeks prior to these meetings and at 6-month intervals between the meetings, these groups will be provided a report that will allow them to assess study progress. Since both groups are composed of study participants, no outcome data will be provided in these reports. The information provided will include data on:

1. Screening, enrollment and retention
2. Patient background characteristics at entry

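### The primary chi-square is valid and the stated power is safe, but it leaves out the outcome's own baseline score; adjusting for it is a small, optional gain

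*Combined protocol and SAP*

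**What the plan says.** - **Test.** Under XIII.F every randomised participant is a success or a failure on each outcome, with drop-outs as failures. The proportions "will be compared between the two groups (Intervention vs. Control) using a chi-square analysis". No covariate or site term is named, and these tests are declared the primary and major secondary efficacy analyses.
- **Baseline.** Section III.A places the baseline assessments before the five-session training and randomisation: "Baseline evaluations will be performed only in those participants who have passed all screening criteria to this point". Section IX confirms what they cover: "The two primary, major secondary and secondary outcomes are measured at baseline".
- **Where baseline is a covariate.** Only in the secondary repeated-measures models of XIII.G, "with baseline scores, plus any variables determined from the baseline comparisons, being used as covariates in the analyses".
- **Covariate rule.** XIII.D: "Any variable that appears to be different between the groups" at p<0.10 becomes a candidate covariate. The sentence does not say for which analyses. XIII.I repeats the idea for the outcome measures in general.
- **Site.** IV.B: "An Interactive Touch Tone Randomization System (ITTRS) will be used for randomization within" each site. Blocking is not described. Sites are expected to randomise 4 to 24 participants each.
- **Control rate.** Table 7 assumes 10%. The feasibility phase in XIII.C exists in part "In order to confirm the hypothesized control proportion for the two primary and major secondary outcomes", and the same section calls a higher rate highly unlikely.

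**The concern.** Success on all three outcomes is defined by change from baseline. When scores fluctuate, participants who start with poor scores tend to improve without treatment. Baseline therefore predicts who is counted as a responder, and using it in the test can recover some precision from data the trial already holds. At stake is efficiency, not validity.

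The second issue is wording. The p<0.10 rule is not expressly confined to secondary analyses, so a reader could ask whether the primary test might be adjusted after an imbalance has been seen.

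**Working it through.** **1. The plan's own figure.** Inputs from Table 7 for MCS: control 0.100, intervention 0.333, two-sided alpha 0.025, power 80%, continuity-corrected. Here Δ = 0.233 and the mean rate is 0.2165.

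- n0 = [2.2414·√(2·0.2165·0.7835) + 0.8416·√(0.1·0.9 + 0.333·0.667)]² / 0.233² = 58.1
- Corrected n = (n0/4)·[1 + √(1 + 4/(n0·Δ))]² = 66.4, so 67; and 67/0.85 = 78.8, so 79

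The same steps give 60/71 for SCI-QOL and 66/78 for fat mass. Table 7 is reproduced exactly.

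**2. Is the stated power safe?** Exact binomial power for MCS at 80 per group is 92.9% for the uncorrected chi-square. With 15% drop-outs counted as failures (rates 0.085 and 0.283) it is 86.5%. XIII.F does not say whether its chi-square is continuity-corrected; if it is, the two figures are 89.6% and 81.0%. All are above the stated 80%.

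**3. How strongly does baseline predict response?** The documents give no correlation. Suppose controls do not change on average and the scale SD, S, is the same at both visits. Then the absolute correlation between baseline and change is SD(change)/(2S). The control rate fixes SD(change) = 4/z, where z is the normal quantile for that rate. With S = 10 assumed (range 12 to 8):

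| Control rate | SD(change) | Correlation, S = 10 | Range |
|---|---|---|---|
| 10% | 4/1.2816 = 3.12 | 0.16 | 0.13–0.20 |
| 20% | 4/0.8416 = 4.75 | 0.24 | 0.20–0.30 |
| 30% | 4/0.5244 = 7.63 | 0.38 | 0.32–0.48 |

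**4. Power, MCS.** Simulated at 80 per group, alpha 0.025: uncorrected chi-square against a logistic score test of arm adjusted for own baseline. The main runs used 20,000 trials per cell, with assumed site sizes and a site SD of 0 to 0.6 on the probit scale. The last column is a separate run of 40,000 trials per cell.

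| Rates | Chi-square power | Gain from own baseline, points | Separate run |
|---|---|---|---|
| 10% vs 33.3% | 92.4–93.7% | +0.1 to +0.4 | 92.9 to 93.1% |
| Same, 15% drop-outs as failures | 85.9–87.4% | +0.2 to +0.4 | 86.5 to 86.8% |
| 20% vs 43.3% | 83–85% | +1.0 to +1.5 | 83.7 to 84.9% |
| 30% vs 53.3% | 78–80% | +2.8 to +4.5 | 78.2 to 82.2% |

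Adjustment never lost power in these single-look runs. Size was 1.5–2.8% for the chi-square and 1.5–2.9% for the adjusted test (nominal 2.5%, simulation error about 0.1 point). With the two-look boundaries of Table 15, power at 10% vs 33.3% was 91.1–92.4% against 91.2–92.3%, which is no visible difference. With the boundaries of Tables 15 and 16, overall size was 1.4–2.4% against 1.6–2.8%.

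**5. The other two outcomes.** SCI-QOL: T-scores have SD 10 (IX.F). Assume a mean sum of 150, a sum SD of 17.3 to 30, and success when follow-up is at most 0.9 times baseline. A 10% control rate then implies a criterion SD of 15/1.2816 = 11.7 and a correlation of only −0.05 to 0.22. Chi-square power for 10% vs 42% is already about 99.6%, so there is nothing to gain. Fat mass was not simulated. By the approximation effective n = n/(1 − R²), with R² of 0.02 assumed, power goes from 94.7% to 95.2%.

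**6. Site.** Adding site strata to the baseline-adjusted test changes power as follows (points):

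| Site SD (probit) | Blocked within site | Not blocked |
|---|---|---|
| 0 | −0.3 to −0.2 | −2.3 to −1.3 |
| 0.3 | +0.3 to +1.0 | −1.2 to −0.5 |
| 0.6 | +1.0 to +3.3 | +0.8 to +2.8 |

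A site SD of 0.6 is a latent intraclass correlation of 0.36/1.36 = 0.26, which is large. At 0 to 0.05, stratifying by site alone changed power by 1 point or less. The sign depends on facts the documents do not give.

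**7. The p<0.10 rule.** With six independent balanced variables (assumed), at least one is flagged by chance in 1 − 0.9⁶ = 47% of trials. Reporting the better of the chi-square and the adjusted result would add 0.2 to 0.5 point to size.

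**The case against.** The strongest reply is that nothing needs repair. Hypotheses, sample size and test all use simple proportions, and baseline already enters through the definition of success. At the plan's rates the gain is under half a point, and part of it is only that the adjusted test is slightly less conservative. The larger gains need control rates that XIII.C calls highly unlikely. All of this stands, and it is why the point is minor. It does not make the 10% rate certain, since the plan itself sets out to confirm it. The uncontrolled pilot's MCS change SD of 17.02 (section I.C, 11 participants) would put 1 − Φ(4/17.02) = 41% at 4 points or more with no mean shift. That is not an estimate of the control rate, but it shows that 10% is not secure.

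A second reply is timing. The protocol version is dated July 2021, after the enrolment years in Table 5, and the DMC sees outcome results during the trial. This also stands: the choice must be made by people who have not seen outcomes by arm.

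Three stronger readings are tempting and are not supported:

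- *That the chi-square is invalid because randomisation is within site.* It held its size in simulation, and was conservative (1.5–1.9%) when allocation was balanced or blocked within site and sites differed strongly.
- *That leaving out site is an error.* Blocking and between-site variation are not stated, and the effect on power changes sign with them.
- *That the primary result may be adjusted at will.* XIII.F fixes a test that takes no covariates, XIII.G is the only place where the flagged variables are used, and XIII.I refers the primary analyses back to section F and asks for the chi-square p-value. Only an express limit is missing.

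**Conclusion.** The point holds as a minor, optional improvement. The primary and major secondary tests are valid and the stated power is safe. They leave unused a baseline score that is already collected and that costs no power to use. For MCS the gain is near zero at the plan's rates and reaches about 3 to 4.5 points only if the control rate is near 30%. For SCI-QOL it is negligible at the plan's rates; for fat mass it is expected to be equally small, though not simulated. The sizes rest on an assumed scale SD of 8 to 12, no average change in controls, and assumed site sizes and site variation. The p<0.10 rule needs a clarification, not a correction. Site stratification is not established as a needed change.

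**What to change.** In XIII.F, before unblinding:

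1. Pre-specify each responder comparison as a logistic score test of arm adjusted for that outcome's own baseline value. Use the same test at the interim look proposed in XIII.I and at the final look.
2. Report a standardised risk difference from the same model. Keep the plain chi-square as a sensitivity analysis and say whether it is continuity-corrected.
3. Align the p-value in Table 13.
4. State in the same place that the p<0.10 rule in XIII.D and XIII.I does not apply to the primary and major secondary tests.
5. Optional: stratify by site only if allocation is blocked within site, pooling small sites by a rule fixed in advance. Avoid 15 separate site terms: at a 10% rate a site of four has no success with probability 0.9⁴ = 66%. Without blocking, stratification can lose up to about 2 power points.

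If the people making the change have already seen outcomes by arm, keep the chi-square as primary and add the adjusted test as a sensitivity analysis only.

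Cost: SAP wording and one regression per outcome, so a little more analysis work. No new data, visits or participants are needed.
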